12.1.3 Reporting period

Details of all AEs (except those listed above) will be documented and reported from the date of commencement of protocol defined treatment until 5 years post-randomisation.

12.2 Reporting Procedure

12.2.1 Site

12.2.1.1 Adverse Events

Protocol-related AEs should be recorded in the AE section of the Treatment Form and Annual Followup Form with reference to the defined Surgical Complications and Definitions (see Appendix 4).

SAEs will be reviewed using the Common Terminology Criteria for Adverse Events (CTCAE), version 4.0 (see Appendix 3). Any SAEs experienced by the patient but not included in the CTCAE should be graded by an Investigator and recorded on the AE Form using a scale of (1) mild, (2) moderate or (3) severe. For each sign/symptom, the highest grade observed since the last visit should be recorded.

12.2.1.2 Serious Adverse Events

For more detailed instructions on SAE reporting refer to the SAE Form Completion Guidelines contained in section 5 of the Investigator Site File (ISF).

AEs defined as serious and which require reporting as an SAE (excluding events listed in Section 12.1.2 above) should be reported on an SAE Form. When completing the form, the Investigator will be asked to define the causality and the severity of the AE which should be documented using the CTCAE version 4.0.

On becoming aware that a patient has experienced an SAE, the Investigator (or delegate) must complete, date and sign an SAE Form. The form should be faxed together with a SAE Fax Cover Sheet (or emailed where fax facilities are not available) to the SMALL Trial Office using one of the numbers listed below as soon as possible and no later than 24 hours after first becoming aware of the event:

To report an SAE, fax the completed SAE Form with an SAE Fax Cover Sheet to:

≞ [name] or ≞ [name]

Or email to:

⊠ [contact]

On receipt the SMALL Trial Office will allocate each SAE a unique reference number. This number will be transcribed onto the SAE Fax Cover Sheet which will then be faxed back to the site as proof of receipt. If confirmation of receipt is not received within 1 working day please contact the SMALL Trial Office. The SAE reference number should be quoted on all correspondence and follow-up reports regarding the SAE. The SAE Fax Cover Sheet completed by the SMALL Trial Office should be filed with the SAE Form in the ISF.

For SAE Forms completed by someone other than the Investigator, the Investigator will be required to countersign the original SAE Form to confirm agreement with the causality and severity assessments. The form should then be returned to the SMALL Trial Office in the post and a copy kept in the ISF.

Investigators should also report SAEs to their own Trust in accordance with local practice.

12.2.1.3 Provision of follow-up information

Patients should be followed up until resolution or stabilisation of the event. Follow-up information should be provided on a new SAE Form (refer to the SAE Form Completion Guidelines for further information).

12.2.2 Trial Office

On receipt of an SAE Form seriousness and causality will be determined independently by a Clinical Coordinator. An SAE judged by the Investigator or Clinical Coordinator to have a reasonable causal relationship with the trial treatment will be regarded as a related SAE. The Clinical Coordinator will also assess all related SAEs for expectedness. If the event is unexpected (i.e. is not defined in the protocol as an expected event) it will be classified as an unexpected and related SAE.

12.2.3 Reporting to the main Research Ethics Committee

12.2.3.1 Unexpected and Related Serious Adverse Events

The Trial Office will report all events categorised as Unexpected and Related SAEs to the main Research Ethics Committee (REC) and Sponsor within 15 days.

12.2.3.2 Other safety issues identified during the course of the trial

The main REC and Sponsor will be notified immediately if a significant safety issue is identified during the course of the trial.

12.2.4 Investigators

Details of all Unexpected and Related SAEs and any other safety issue which arises during the course of the trial will be reported to Principal Investigators. A copy of any such correspondence should be filed in the ISF.

12.2.5 Data Monitoring Committee

The independent Data Monitoring Committee (DMC) will review all SAEs.

13. DATA HANDLING AND RECORD KEEPING

13.1 Data Collection

The Case Report Form (CRF) will comprise the following forms:

Form	Summary of data recorded	Schedule for submission
Eligibility Checklist	Confirmation of eligibility	As soon as possible after randomisation
Randomisation	Patient details; confirmation of diagnosis of grade 1 ER-pos, PR-pos, HER2-neg breast cancer	As soon as possible after randomisation
Baseline	Details of biopsy histology; details of planned surgery, concomitant medications	Within 1 month of randomisation
Surgical Procedure for Surgery Arm	Details of type of surgery performed, surgical complications Details of any additional procedure performed, surgical complications	Following completion of planned primary surgery (allow 30 days to report surgical complications) Following completion of any additional procedures
Pathology – Planned Randomised Surgery	Pathology details of surgical excision specimen (including margin status) and axillary node status, (with copy of pathology report)	As soon as possible following surgery
Pathology – Incomplete Surgical Excision	Pathology details of any re-excision of margins (with copy of pathology report)	As soon as possible following re-excision procedure
VAE	Details of VAE, including needle gauge used, post-procedure radiology (including any repeat imaging or haematoma aspiration)	Following completion of planned VAE and post- VAE mammogram (allow 30 days to report surgical complications)

UNIVERSITY^{OF} BIRMINGHAM

Radiological Second Opinion Service Request	Details of imaging submitted and reason for second opinion request	As required
Pathology – Planned Randomised VAE	Pathology details following planned randomised VAE (with copy of pathology report)	As soon as possible following VAE
Surgical Procedure for VAE Arm	Details of type of surgery performed, surgical complications	Following completion of any additional procedures
	Details of any additional procedure performed in VAE arm, surgical complications	
Pathology – Following Incomplete VAE	Pathology details for any surgery following radiological diagnosis of incomplete excision or upon upward grade migration post VAE (with copy of pathology report)	As soon as possible following procedure
Adverse Event	Complications related to planned randomised treatment	As soon as possible following 30 days after completion of randomised treatment
Adjuvant Treatment	Details of adjuvant endocrine therapy and radiotherapy, targeted therapy and chemotherapy. Details of any related adverse events.	Within 1 month of the 6- month follow-up
Annual Follow-up	Survival, outcome of annual mammogram, concomitant medications (HRT, endocrine therapy, NSAIDs), persisting protocol related adverse effects, record of related interventions and referrals, new breast disease, other clinical trials	Within 1 month of patient annual mammogram or as soon as possible following investigations or treatment if indicated
Ipsilateral Invasive Breast Cancer	Date confirmed, disease type and nature (e.g. in situ or invasive), including grade and type (with copy of pathology report)	Immediately upon confirmation of disease
Pathology – Invasive Ipsilateral Breast Cancer	Details of pathology of ipsilateral breast cancer	As soon as possible following confirmation of ipsilateral invasive breast cancer
Contralateral Invasive Breast Cancer	Date confirmed, disease type and nature including grade and type	Immediately upon confirmation of disease
Death Form	Date and cause of death	Immediately upon notification of patient's death
Deviation Form	Completed in the event of a deviation from the protocol	Immediately upon discovering deviation
Withdrawal Form	Used to notify the Trial Office of patient withdrawal from the trial	Immediately upon patient withdrawal
Serious Adverse Event	See Section 12	Complete and return form immediately on discovering the patient has experienced an SAE

UNIVERSITY^{OF} BIRMINGHAM

The study will use an eRDC system (as described in Section 6.2) for completion of CRFs. If the eRDC system is unavailable for an extended period of time a paper based CRF should be completed and forms returned to the SMALL Trial Office. The Investigator and site staff must ensure all data from scheduled visits are promptly entered into the eRDC system in accordance with the SMALL electronic CRF (eCRF) Completion Guidelines. The SMALL eRDC system can be accessed via the following link:

http://www.cancertrials.bham.ac.uk

SAE reporting will be paper-based. Paper CRFs must be completed, signed/dated and returned to the SMALL Trial Office by the Investigator or an authorised member of the site research team (as delegated on the Site Signature and Delegation Log) within the timeframe listed above. The exceptions to this are the SAE Form and Withdrawal of Consent Form which must be co-signed by the Investigator. Entries on the CRF should be made in ballpoint pen, in blue or black ink, and must be legible. Any errors should be crossed out with a single stroke, the correction inserted and the change initialled and dated. If it is not obvious why a change has been made, an explanation should be written next to the change.

Data reported within the eRDC system or on paper should be consistent with the source data or the discrepancies should be explained. If information is not known, this must be clearly indicated on the form. All missing and ambiguous data will be queried. All sections are to be completed before returning to the SMALL Trial Office.

In all cases it remains the responsibility of the Investigator to ensure that the CRF has been completed correctly and that the data are accurate.

Where paper CRFs have been used, the completed original forms must be sent to the SMALL Trial Office. A copy of all CRFs should be retained in the ISF.

Study CRFs may be amended by the SMALL Trial Office, as appropriate, throughout the duration of the study. Whilst this will not constitute a protocol amendment, new versions of the form must be implemented by participating sites immediately on receipt.

13.2 Archiving

It is the responsibility of the Principal Investigator to ensure all electronically stored data, essential trial documentation and source records (e.g. signed Informed Consent Forms, Investigator Site Files, Pharmacy Files, patients' hospital notes, copies of CRFs etc.) at their site are securely retained for at least 10 years after the end of the trial or following the processing of all biological material collected for research, whichever is the later. Do not destroy any documents without prior approval from the CRCTU Document Storage Manager.

14. QUALITY MANAGEMENT

14.1 Site Set-up and Initiation

All sites will be required to sign a Clinical Study Site Agreement and complete a Site Registration Form prior to participation. In addition, all participating Investigators will be asked to complete a Registration Form and supply a current CV to the SMALL Trial Office. All members of the site research team will also be required to sign the Site Signature and Delegation Log, which should be returned to the Trial Office. Prior to commencing recruitment all sites will undergo a process of initiation. Key members of the site research team will be required to attend either a meeting or a teleconference covering aspects of the trial design, protocol procedures, Adverse Event reporting, collection and reporting of data and record keeping. Sites will be provided with an Investigator Site File containing essential documentation, instructions, and other documentation required for the conduct of the trial. The Trial Office must be informed immediately of any change in the site research team.

14.2 On-site Monitoring

Monitoring will be carried out as required following a risk assessment and as documented in the SMALL Quality Management Plan. Additional on-site monitoring visits may be triggered for example by poor CRF return, poor data quality, low SAE reporting rates, excessive number of patient withdrawals or deviations. If a monitoring visit is required the Trial Office will contact the site to arrange a date for the proposed visit and will provide the site with written confirmation. Investigators will allow the SMALL trial staff access to source documents as requested.

14.3 Central Monitoring

Where a patient has given explicit consent, sites are requested to send in copies of signed Informed Consent Forms for in-house review.

Trial staff will be in regular contact with the site research team to check on progress and address any queries that they may have. Trial staff will check CRFs for compliance with the protocol, data consistency, missing data and timing. Sites will receive Data Clarification Forms requesting missing data or clarification of inconsistencies or discrepancies.

Sites may be suspended from further recruitment in the event of serious and persistent non-compliance with the protocol and/or GCP, and/or poor recruitment. Any major problems identified during monitoring may be reported to the Trial Management Group, Trial Steering Committee and the relevant regulatory bodies. This includes reporting serious breaches of GCP and/or the trial protocol to the main Research Ethics Committee (REC).

14.4 Audit and Inspection

The Investigator will permit trial-related monitoring, audits, ethical review, and regulatory inspection(s) at their site, providing direct access to source data/documents.

Sites are also requested to notify the Trial Office of any inspections.

14.5 Notification of Serious Breaches

In accordance with Regulation 29A of the Medicines for Human Use (Clinical Trials) Regulations 2004 and its amendments the Sponsor of the trial is responsible for notifying the licensing authority in writing of any serious breach of:

- The conditions and principles of GCP in connection with that trial or;
- The protocol relating to that trial, within 7 days of becoming aware of that breach

For the purposes of this regulation, a "serious breach" is a breach which is likely to effect to a significant degree:

- The safety or physical or mental integrity of the subjects of the trial; or
- The scientific value of the trial

Sites are therefore requested to notify the SMALL Trial Office of a suspected trial-related serious breach of GCP and/or the trial protocol. Where the Trial Office is investigating whether or not a serious breach has occurred sites are also requested to cooperate with the Trial Office in providing sufficient information to report the breach to the MHRA where required and in undertaking any corrective and/or preventive action.

15. END OF TRIAL DEFINITION

The end of trial will be 6 months after the last data capture, or the final analysis of predictive biomarkers, whichever is later. This will allow sufficient time for the completion of protocol procedures, data collection and data input.

The duration of time for which patient follow-up data will be collected is dependent on future funding arrangements. Current funding is secured for this to continue for 5 years after randomisation of each patient and further funding will be sought to continue this in the longer term.

The Trial Office will notify the main REC that the trial has ended and a summary of the clinical trial report will be provided within 12 months of the end of trial.

16. STATISTICAL CONSIDERATIONS

16.1 Internal Pilot Study

The first part of the SMALL trial is an internal pilot study of 18 months duration. The aim of the internal pilot study is to demonstrate that sufficient eligible patients can be identified and recruited over the course of the study to robustly answer the main trial objectives. The patients randomised during the internal pilot phase will form part of the total number of patients (800) included in the main study.

16.1.1 Definition of outcome measures

The outcome measures in the internal pilot study will be assessed at the end of the 18 month pilot:

• Adequate recruitment is defined in terms of the number of sites open and the number of patients randomised at conclusion of the internal pilot phase

16.1.2 Analysis

No formal statistical testing will take place during the feasibility phase. Recruitment and site opening will be monitored by the Trial Management Group throughout the pilot phase. The specific progression criteria are detailed below in Section 16.1.3.

16.1.3 Specific progression criteria from internal pilot to main trial

- 141 patients recruited by end of month 18
- 44 sites activated for recruitment by the end of month 18

16.2 Main Trial

16.2.1 Definition of Primary outcome measures

Primary Outcome 1: Re-excision following initial procedure

The requirement for a second procedure in both arms will be ascertained.

Following VAE, patients will undergo radiological assessment of completeness of excision of their primary tumour. Where there is radiological evidence of residual disease, patients will undergo standard surgical excision (wide local excision and sentinel lymph node biopsy).

In the standard surgery arm of the trial, histopathological assessment of resection margin status will be carried out. The need for re-excision of margins will be determined by local MDT policy.

Primary Outcome 2: Local recurrence free survival time for VAE

This is defined in whole days as the time from randomisation until first report of ipsilateral invasive breast cancer. Patients without recurrence will be censored at the date of last clear mammogram or date of death.

16.2.2 Definition of Secondary outcome measures

Complications arising from surgery or VAE

This is defined as complications occurring within 30 days of protocol defined surgery or VAE. Possible complications are expected to include seroma, haematoma, wound infections, delayed wound healing, skin flaps necrosis, nipple necrosis, wound dehiscence, in hospital complications, hospital readmission and unplanned re-operations, and these are defined in Appendix 4.

Time to ipsilateral breast cancer recurrence

This is defined in whole days as the time from randomisation until first report of ipsilateral invasive disease. Randomised patients with no evidence of disease will be censored at the date of last clear mammogram or date of death.

Time to development of contralateral invasive breast cancer

This is defined in whole days as time from randomisation until first report of contralateral invasive disease. Randomised patients with no evidence of disease will be censored at the date of last clear mammogram or date of death.

Overall survival time

This is defined in whole days as time from randomisation until date of death from any cause. Patients who remain alive during the course of the study will be censored at the date last known to be alive.

Quality of life

The assessment utilities being used are defined in Section 8.1. These will all be scored at each timepoint utilising the specific scoring schemes for each type of questionnaire which will produce scores across multiple themes and domains.

QALY

This will be calculated from the EQ5D QoL questionnaire and will be utilised in the Health Economic analysis (see Section 9).

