surgery in a selected low-risk patient population has suggested that this approach is safe with acceptable recurrence-free survival¹⁴, and this is currently being further investigated in the SOUND trial¹⁵ in a comparable patient group. Taken together, this data suggests a lack of evidence to justify routine use of SLNB in this setting, given that it has an attendant (albeit low) morbidity in terms of lymphoedema, numbness and paraesthesia^{16,17}.

Minimally invasive approaches to the treatment of small breast cancers

Given that many of the biologically favourable small tumours in the population eligible for the SMALL trial are likely to represent overdiagnosis, there is no prospective evidence that conventional open surgery is required. Thus, it is increasingly important that novel, minimally invasive techniques be developed for use in this setting. Such techniques may potentially reduce the morbidity and complication rates outlined above, as well as healthcare costs. A recent meta-analysis of minimally-invasive image-guided percutaneous ablation techniques for the treatment of breast cancer concluded that such techniques have a high rate of technical success, with relatively low complication rates¹⁸. However, many of the techniques described in this review are not in general use within the UK, and would not be available for routine use in the context of the NHSBSP. Furthermore, evidence from prospective randomised trials will be required to support the adoption of such techniques into clinical practice, enabling women of screening age to make informed choices about their treatment.

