1.2 Trial Rationale

1.2.1 Justification for patient population

The patient population are women of NHSBSP age or above (as these women can still access the screening programme) who have had a small, good-prognosis tumour detected mammographically. It is now possible to identify women with screen-detected breast cancers who have an extremely good prognosis (low grade, ER positive, progesterone receptor (PR) positive and human epidermal growth factor receptor type 2 (HER2) negative tumours), and this is the patient population most likely to be overtreated by conventional surgical excision. The recent IMPORT LOW trial has demonstrated that with surgery followed by standard adjuvant therapies extremely low local recurrence rates can be achieved²⁵. It is now necessary to investigate whether the extent of surgical intervention in this patient group can be further reduced, by utilising a minimally-invasive radiologically guided technique for the excision of these primary tumours and omitting axillary surgery. This approach has the potential to benefit patients by avoiding a general anaesthetic and an open procedure (as well as being a more convenient treatment option), together with the possibility of reducing surgical complications and the side effects associated with surgery. Furthermore, there are potential important benefits to the NHS, in terms of reducing theatre time requirements (freeing up operating time for other procedures), and cost savings associated with both the avoidance of surgery and possibly also from the avoidance of the need to manage long-term surgical complications such as lymphoedema.

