7.1.6 Related adverse event review

Protocol-related adverse events (AEs) will be collected post trial treatment, at 6-months post randomisation and annually from randomisation on the CRF from years 1-5, with reference to the defined Surgical Complications and Definitions (see Appendix 4) for events occurring within 30 days of trial treatment or CTCAE thereafter. Serious Adverse Events (SAEs) will be reported from trial entry until 5 years post-randomisation in accordance with Section 12 Adverse Event Reporting.

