16.3 Analysis of Outcome Measures

Key aspects of the analysis methods to be utilised are detailed below and the statistical analysis plan will provide details of the selection of subjects to be included in each analysis in addition to procedures accounting for missing, unused or spurious data.

Primary Outcomes

Re-excision following initial procedure

Once all patients have undergone surgery the proportion of patients requiring re-excision will be compared between the trial arms. A 2-sided 95% confidence interval around the difference in proportions will be calculated. If the upper bound of the confidence interval is below 10 then non-inferiority will be declared. If non-inferiority is declared then a pre-specified but unpowered analysis of superiority will also be undertaken, to investigate whether superiority has also been demonstrated.

Local recurrence free survival time for VAE

The point estimate for local recurrence free survival at 5 years will be calculated with 2-sided 95% confidence interval using the Kaplan-Meier method. No hypothesis testing will be performed. This will be interpreted both with reference to the same rate calculated for the surgery arm of the trial and in relation to the undesirable local recurrence rate of 97%. Sensitivity analysis will be conducted utilising exact methods for calculating the proportion of recurrence at 5 years to explore the appropriateness of the Kaplan-Meier method.

Secondary Outcomes

Time to ipsilateral breast cancer recurrence, time to development of contralateral invasive breast cancer and overall survival will be analysed as per local recurrence free survival time above. Complications arising from surgery or VAE will be reported descriptively for both treatment arms (see Appendix 4 for complications and definitions). No hypothesis testing will be conducted.

QoL will be analysed using standardised area under the curve and appropriate repeated measures modelling techniques to compare treatment arms.

Page 31 of 49

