16.6 Planned Final Analyses

The final analysis of re-excision following initial procedure will be conducted 3 months following the completion of recruitment. This will ensure all patients have undergone randomised procedures and been assessed for re-excision. The analysis of complications arising from surgery or VAE will also be conducted at this point. Analysis of the local recurrence free survival and all remaining secondary outcomes will be conducted 3 months after all patients have completed 3 years of annual mammography following randomisation.

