APPENDIX 4 – SURGICAL COMPLICATIONS & DEFINITIONS

Post-operative complications occurring within 30 days;

- 1. Seroma (breast/axilla) a collection of serosanginous fluid in the wound
 - a. Requiring aspiration 1-2 times
 - b. Requiring aspiration 3 or more times
- 2. Haematoma (breast/axilla) a collection of blood in the wound
 - a. Minor (conservative management)
 - b. Major 1 requiring evacuation in clinic +/- US guidance (no GA)
 - c. Major 2 requiring surgical evacuation (GA)
- 3. Wound infection (breast/axilla)
 - a. Minor (oral antibiotics)(breast/axilla)
 - b. Major 1 (iv antibiotics)(breast/axilla)
 - c. Major 2 (surgical drainage +/- debridement)(breast/axilla)
- 4. Delayed wound healing/skin flap necrosis
 - a. Minor (conservative management)
 - b. Major 1 requiring surgical debridement in clinic (no GA)
 - c. Major 2 requiring surgical debridement in theatre (GA)
- 5. Nipple necrosis
 - a. Minor (conservative management)
 - b. Major 1 (requiring debridement)
 - c. Major 2 (complete NAC loss)
- 6. Wound dehiscence (breast/axilla)
 - a. Minor (conservative management)(breast/axilla)
 - b. Major (requiring return to theatre)(breast/axilla)
- 7. In-hospital complication (including systemic complications
 - a. DVT/PE/MI/LRTI/UTI/transfusion/unplanned HDU/ITU admission
- 8. Readmission to hospital within 30 days
 - a. No
 - b. Yes, for complication listed above (1-7)
 - c. Yes, for other reason

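### The only clinician-reported safety outcome ends at 30 days and lists no lymphoedema or arm sensory event; later related events are coded differently by arm and have no named between-arm summary

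*Protocol*

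**What the plan says.** All references are to the Protocol.

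**Rationale.** Section 1.1 argues against routine sentinel node biopsy in this setting because "it has an attendant (albeit low) morbidity in terms of lymphoedema, numbness and paraesthesia". Section 1.2.1 lists, as a possible source of savings, "avoidance of the need to manage long-term surgical complications such as lymphoedema".

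**Outcome.** Post-procedure complications are the first secondary objective in the synopsis. Section 16.2.2 defines the outcome: "This is defined as complications occurring within 30 days of protocol defined surgery or VAE". Appendix 4 is headed "Post-operative complications occurring within 30 days". It covers seroma, haematoma, infection, healing and flap problems, nipple necrosis, dehiscence, in-hospital events and readmission.

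**Analysis.** Section 16.3 states: "Complications arising from surgery or VAE will be reported descriptively for both treatment arms (see Appendix 4 for complications and definitions". Section 16.6 first sets the re-excision analysis at 3 months after recruitment ends and then adds: "The analysis of complications arising from surgery or VAE will also be conducted at this point".

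**Later collection.** Section 7.1.6 (surgery arm) says: "Protocol-related adverse events (AEs) will be collected post trial treatment, at 6-months post randomisation and annually from randomisation on the CRF from years 1-5". Section 7.2.5 sets the same times for the VAE arm, and section 12.1.3 runs reporting to 5 years. Section 13.1 summarises the relevant content of the Annual Follow-up Form as "persisting protocol related adverse effects, record of related interventions and referrals".

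**Patient-reported data.** Section 8.1.1 describes BR23 as covering breast and arm symptoms. Table 2 schedules it at baseline, 6, 12, 36 and 60 months. Section 16.3 compares quality of life between arms. The Schedule of Events restricts the questionnaires to women who consent to the quality-of-life sub-study.

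**The concern.** The arms differ by design in axillary surgery. Every surgery-arm woman is due sentinel node biopsy (7.1.2.1). After VAE, only women who go on to surgery are, because of incomplete excision or regrading to grade 3 (7.2.2.1). The protocol itself names the late morbidity of that procedure as something VAE may spare. Its clinician-reported safety outcome closes too early to see such morbidity and has no term for it.

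Two things are at stake:

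- The complications objective would be answered for early wound and systemic events only.
- The later related events that sites are asked to record might not be comparable between arms, because the protocol points the two arms to different dictionaries after day 30. A table specified in a SAP cannot recover events that were coded to an unsuitable list or not prompted for.

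**Working it through.** The protocol has no figure on this point to reproduce, so the main check sets its passages side by side.

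**1. Coverage of the three named effects**

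| Source | Window | Lymphoedema, numbness, paraesthesia |
|---|---|---|
| Complications outcome (16.2.2, Appendix 4) | 30 days | No item |
| Related AEs (7.1.6, 7.2.5, 12.1.3) | To year 5 | Can be reported; no summary named in 16.2.2 or 16.3 |
| BR23 (8.1.1, Table 2, 16.3) | To 60 months | Arm symptoms; sub-study women only |

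**2. Coding after day 30**

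- Surgery arm (7.1.6): Appendix 4 up to 30 days, CTCAE afterwards.
- VAE arm (7.2.5): Appendix 4 only, including for years 1 to 5.
- Reporting procedure (12.2.1.1): Appendix 4 for related AEs on both the Treatment and Annual Follow-up Forms; CTCAE is named only for SAEs.

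A non-serious case of lymphoedema at month 9 therefore has a dictionary in the surgery arm under 7.1.6. It has no matching term in the VAE arm under 7.2.5, nor in either arm under 12.2.1.1.

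**3. What a late summary could show**

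Inputs: 267 surgery and 533 VAE women, and 20% re-excision (16.7). The lymphoedema rate *r* after sentinel node biopsy is an assumption, taken as 2%, 5% or 10%. The calculation further assumes no lymphoedema without sentinel node biopsy, full and equal ascertainment, no drop-out, and no extra biopsies from regrading.

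- VAE women having sentinel node biopsy: 0.20 × 533 = 107
- Expected rates: *r* after surgery, 0.2*r* after VAE; difference 0.8*r*
- SE = √[*r*(1 − *r*)/267 + 0.2*r*(1 − 0.2*r*)/533]
- Approximate power, two-sided 5% = Φ(0.8*r*/SE − 1.96)

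| *r* | Cases, surgery (267*r*) | Cases, VAE (533 × 0.2*r*) | Difference (points) | 1.96 × SE (points) | Power |
|---|---|---|---|---|---|
| 2% | 5 | 2 | 1.6 | 1.8 | 43% |
| 5% | 13 | 5 | 4.0 | 2.7 | 81% |
| 10% | 27 | 11 | 8.0 | 3.8 | 99% |

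At 2% the expected interval includes zero; at 5% or 10% it does not.

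**4. Which BR23 data exist at the later analysis**

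Section 16.6 places that analysis 3 months after every woman has completed 3 years, so the last woman recruited is at 36 + 3 = 39 months. A woman needs 60 months of follow-up to have the final questionnaire, so those recruited in about the last 60 − 39 = 21 months of the 48-month recruitment period will not have it. The 36-month questionnaire will be due for all.

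**The case against.** The strongest reply is that late arm morbidity is not ignored. BR23 arm symptoms fall within a listed secondary outcome that is compared between arms. The DMC receives all adverse events (16.5). The annual form also records related interventions and referrals, and section 9.2 collects related care contacts. Section 16.3 gives only key aspects of the analysis, and a by-arm table of AEs is ordinary SAP content. The word 'persisting' comes from a one-line summary of a form that is not shown, and the operative text in 7.1.6 and 7.2.5 does not exclude a new late event.

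Much of this stands. A reader might infer that lymphoedema will go unreported, or that the safety result will show none in either arm. The documents do not support that, because of BR23, the DMC reports and a possible SAP table. A reader might also infer that this is the harm on which the arms differ most. The protocol calls the morbidity low and cites early complication rates of up to 25% after breast-conserving treatment, which the 30-day outcome does address. Nor is there a link to the 10-point re-excision margin: section 16.7 justifies it by patient acceptability, salvage by a second procedure and the absence of survival consequences.

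The reply does not remove the core. The outcome definition, its dictionary, the coding rules and the form content are set in the protocol. Section 16.3 leaves the selection of subjects and the handling of missing, unused or spurious data to the SAP, not the repair of inconsistent coding. BR23 comes from consenting sub-study women only and is not a diagnosis of lymphoedema. DMC review is confidential monitoring, not a trial result.

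**Conclusion.** The point holds in a limited form. The one clinician-reported safety outcome closes at 30 days and has no term for the late axillary morbidity that the rationale cites. Related events after day 30 are collected to year 5, but under coding rules that differ between arms and with no between-arm summary named in the protocol. BR23 arm symptoms in the sub-study are the only planned long-term comparison.

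The textual findings need no assumption. The size does: the protocol gives no lymphoedema rate, and the power figures of 43%, 81% and 99% depend on the assumed 2%, 5% and 10% and on full ascertainment. At the low end, a late summary would probably be inconclusive. The change should be made, because late events that are not prompted for or not coded alike may not be recoverable. The primary outcomes and sample size are unaffected.

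**What to change.** 1. Keep the 30-day complications outcome as it is.
2. Reconcile sections 7.1.6, 7.2.5 and 12.2.1.1 so that related AEs after day 30 are coded the same way in both arms, with a dictionary that has terms for these events.
3. On the Annual Follow-up Form, ask for new or persisting related effects, with prompts for lymphoedema and for arm or axillary numbness and paraesthesia.
4. In 16.2.2 and 16.3, add a descriptive outcome: the proportion of women in each arm with any of these events after 30 days, with the difference and its 95% CI, reported at the later analysis in 16.6.
5. Show BR23 arm symptoms alongside to 36 months, and add the 60-month data only once that follow-up is complete.

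The cost is protocol wording, a small edit to an existing form and one more descriptive table; no visit, procedure or sample-size change is needed. The table should be read with caution, because attribution is open-label and its precision depends on an unknown event rate.
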